## 7.2 Statistical issues

### 7.2.1 Significance level and confidence intervals

90% confidence intervals and p-values will be produced between different treatments. A two-sided significance level of 10% will be considered the level of statistical significance. Confidence intervals and p-values will be presented up to four decimal places.

### 7.2.2 Handling of dropouts or missing data

In general, missing data or partial data will not be imputed, and statistical analyses will be performed for observed cases only. Possible missing data will be included in statistical calculations via mixed models theory, where missing data can be utilized by setting the subject as random effect in the statistical model. Possible sensitivity analyses may be carried out to evaluate the robustness of the statistical results, that is, particularly the impact of potential outliers.

### 7.2.3 Handling of baseline values

Screening visit will be used as a baseline for all post baseline variables. If multiple values of a variable are recorded at screening:

- For safety laboratory measurements the last of these values will be used as baseline.
- For ECG the average of these values will be calculated and used as baseline.

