3.2 Study design

The study will consist of 4 parallel groups (Groups 1-4). All groups will have a crossover design with 4 treatment periods, each lasting for 8 days. The total duration of the study will be approximately 10-15 weeks for each study subject.

The study design is presented in [Figure 1](#) and the study treatments for the 4 groups are presented in [Table 1](#).

Figure 1. Study design

[figure not shown]

Table 1. Summary of study treatments

Group 1	
A1	50 mg of MR levodopa + 12.5 mg of carbidopa
B1	50 mg of MR levodopa + 65 mg of carbidopa
C1	50 mg of MR levodopa + 65 mg of carbidopa + 50 mg of ODM-104
D1	50 mg of MR levodopa + 65 mg of carbidopa + 100 mg of ODM-104
Group 2	
A2	100 mg of MR levodopa + 25 mg of carbidopa
B2	100 mg of MR levodopa + 65 mg of carbidopa
C2	100 mg of MR levodopa + 65 mg of carbidopa + 50 mg of ODM-104
D2	100 mg of MR levodopa + 65 mg of carbidopa + 100 mg of ODM-104
Group 3	
A3	150 mg of MR levodopa + 37.5 mg of carbidopa
B3	150 mg of MR levodopa + 65 mg of carbidopa
C3	150 mg of MR levodopa + 65 mg of carbidopa + 50 mg of ODM-104
D3	150 mg of MR levodopa + 65 mg of carbidopa + 100 mg of ODM-104
Group 4	
A4	100 mg of IR levodopa + 25 mg of carbidopa (Sinemet)
B4	100 mg of MR levodopa + 65 mg of carbidopa
C4	100 mg of MR levodopa + 25 mg of carbidopa + 100 mg of ODM-104
D4	100 mg of MR levodopa + 65 mg of carbidopa + 100 mg of ODM-104

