6.1.1 Procedures during the screening period

Screening procedures will start after receiving approval from the ethics committee (EC) and competent authority (CA).

A prospective subject will receive both written and verbal information about the study and will have an opportunity to ask questions and sufficient time to decide whether or not to participate in the study. A signed and dated written IC for the main study will be obtained prior to any screening activities (see section 11.3). A separate pharmacogenomic (PG) IC will be obtained from subjects who agree to take part in the optional study-related exploratory PG study (see section 6.3).

The screening visit will take place within 21 days before the first study treatment administration.

The following procedures will be performed at the screening visit:

- Physical examination will be performed.
- Demographic data (sex, year of birth, age and racial group), substance use (use of nicotine, alcohol and caffeine, and drug abuse) and weight, height and BMI will be recorded.
- Medical history, current medical conditions and concomitant treatments will be recorded.
- AEs will be recorded.
- BP and HR will be recorded in the supine position after at least 5 min rest.
- 12-lead ECG will be recorded in the supine position after at least 5 min rest.
- Alcohol breath testing will be performed.
- Blood samples for haematology, clinical chemistry and serology will be collected after fasting for at least 10 h; see section 6.4.5 for details.
- Urine drug abuse testing will be performed.
- Urinalysis will be performed.
- Columbia-Suicide Severity Rating Scale (C-SSRS) will be performed.
- Subjects will be instructed to call the study centre when they experience AE or need to take concomitant treatment after the screening visit until the end-of-study visit when they are not in-house.

For practical reasons, the procedures outlined above may be performed on 2 separate occasions, for example, the physical examination may be performed a couple of days later than the other procedures.

A subject will be entered into the study if all of the inclusion criteria and none of the exclusion criteria are met and will be randomised to one of the treatment sequences before starting study treatments.

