6.1.2 Procedures during the treatment periods

6.1.2.1 Days -1 and 1

Subjects will arrive at the study centre in the evening before day 1 (day -1) and stay at the study centre until the 24 h PK blood sample has been collected in the morning of day 8.

The following procedures will be performed on day -1:

- Alcohol breath and urine drug abuse tests will be performed before the first study treatment administration. Use of nicotine-containing products within the previous week will be enquired.
- BP and HR will be recorded in the supine position after at least 5 min rest.
- 12-lead ECG will be recorded in the supine position after at least 5 min rest.

The following procedures will be performed on day 1:

- BP and HR will be recorded in the supine position after at least 5 min rest 0-2 h before the first morning dose.
- 12-lead ECG will be recorded in the supine position after at least 5 min rest 0-2 h before the first dose. 3 recordings will be performed within 5 min (1-2 min interval between the measurements).
- Blood samples for selected haematology and clinical chemistry tests will be collected before the first dose; see section 6.4.5.
- Urinalysis will be performed before the first dose.
- Subjects will take carbidopa and ODM-104 (in study periods including ODM-104) as described in section 5.3.
- Meals will be served as described in section 5.3.
- Current medical conditions and concomitant treatments will be recorded.
- AEs will be recorded.

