6.4.5 Laboratory safety assessments

The following laboratory tests will be taken at the screening visit after at least 10 h of fasting:

Haematology:

- Haemoglobin
- Haematocrit
- Erythrocytes
- Thrombocytes
- Mean corpuscular volume
- Mean corpuscular haemoglobin
- Mean corpuscular haemoglobin concentration
- Leucocytes
- Differential count (lymphocytes, monocytes, eosinophils, neutrophils, basophils)

Clinical chemistry:

- Albumin
- Creatinine
- Alkaline phosphatase
- Alanine aminotransferase

- Aspartate aminotransferase
- Creatine kinase
- Gamma-glutamyl transferase
- Glucose
- Magnesium
- Sodium
- Potassium
- Calcium (albumin corrected)
- C-reactive protein
- Thyroid stimulating hormone
- Total bilirubin

Urinalysis:

- Stick-test: pH, leucocytes¹, nitrites¹, protein, blood¹, glucose (¹ in case of findings, a microscopy examination of urine sediment will be performed)

Serology:

- Human immunodeficiency virus antigen/antibody
- Hepatitis C virus antibodies
- Hepatitis B-surface antigen

Selected laboratory tests

The following selected laboratory tests will be performed on days 1 and 7 in each treatment period, before the first dose:

Haematology:

- Haemoglobin
- Haematocrit
- Erythrocytes
- Thrombocytes
- Mean corpuscular volume
- Mean corpuscular haemoglobin
- Mean corpuscular haemoglobin concentration
- Leucocytes

- Differential count (lymphocytes, monocytes, eosinophils, neutrophils, basophils)

Clinical chemistry:

- Creatine kinase
- Creatinine
- Alkaline phosphatase
- Aspartate aminotransferase
- Gamma-glutamyl transpeptidase
- Alanine aminotransferase
- Total bilirubin
- Sodium
- Potassium
- Magnesium
- C-reactive protein

Urinalysis

- Stick-test: pH, leucocytes¹, nitrites¹, protein, blood¹, glucose (¹in case of findings, a microscopy examination of urine sediment will be performed)

End-of-study laboratory tests

The same laboratory tests as at the screening visit, except determination of thyroid stimulating hormone and albumin, serology tests, urine test for drug abuse and alcohol breath test will be performed.

Alcohol and drug abuse tests during the study

An alcohol breath test will be performed at the screening visit and on admission in each treatment period.

A urine drug abuse test will be performed at the screening visit and on admission in each treatment period.

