8.4.5.2 Clinical safety analysis

Vital signs (systolic and diastolic BP and HR) at each visit and change from baseline (screening value) in each vital sign will be summarised using descriptive statistics. 12-lead ECG parameters at each time point and change from baseline (screening value) will be summarised using descriptive statistics. Physical examination and C-SSRS findings will be tabulated.

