#### **8.5.2 Laboratory safety variables**

Laboratory values and changes from baseline (screening value) in laboratory values will be summarised using descriptive statistics. The number and proportion of subjects with laboratory values outside the normal range will be summarised by visit for each laboratory analyte. Unscheduled laboratory measurements will not be used in tables. They will be included in the listings.

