### 14.3 Safety data

|                |  |
|----------------|--|
| Table 14.3.1.1 | Summary of adverse events during study treatment (subject and event count) |
| Table 14.3.1.2 | Adverse events during study treatment (subject and event count)            |

|                  |   |
|------------------|---|
| Table 14.3.1.3   | Adverse events during study treatment by severity (subject count)                     |
| Table 14.3.1.4   | Adverse events related to study treatment (subject and event count)                   |
| Table 14.3.1.5   | Adverse events during study treatment by severity and causality (event count)         |
| Table 14.3.1.6   | Adverse events before start of study treatment (subject and event count)              |
| Table 14.3.1.7   | Adverse events at the end of study (subject and event count)                          |
| Table 14.3.2.1   | Summary listing of deaths, other serious and significant adverse events               |
| Table 14.3.2.2   | Listing of deaths   |
| Table 14.3.2.3   | Listing of serious adverse events   |
| Table 14.3.2.4   | Listing of adverse events leading to premature discontinuation                        |
| Table 14.3.2.5   | Listing of other significant adverse events   |
| Table 14.3.2.6   | Listing of special situations   |
| Table 14.3.3.1   | Summary listing of narratives of deaths, other serious and significant adverse events |
| Table 14.3.4     | Listing of significant abnormal laboratory values                                     |
| Table 14.3.5.1.1 | Haematology   |
| Table 14.3.5.1.2 | Changes from baseline in haematology  |
| Table 14.3.5.1.3 | Shift tables for haematology variables  |
| Table 14.3.5.2.1 | Chemistry   |
| Table 14.3.5.2.2 | Changes from baseline in chemistry  |
| Table 14.3.5.2.3 | Shift tables for chemistry variables  |
| Table 14.3.5.3   | Serology  |
| Table 14.3.5.4.1 | Urinalysis  |
| Table 14.3.5.4.2 | Shift tables for urinalysis variables - Safety population                             |
| Table 14.3.6.1.1 | Supine heart rate (bpm)   |
| Table 14.3.6.1.2 | Changes from baseline in supine heart rate (bpm)                                      |
| Table 14.3.6.2.1 | Supine diastolic blood pressure (mmHg)  |
| Table 14.3.6.2.2 | Changes from baseline in supine diastolic blood pressure (mmHg)                       |
| Table 14.3.6.3.1 | Supine systolic blood pressure (mmHg)   |

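### Vital-sign and laboratory changes in all four crossover periods are measured from one screening value, although pre-dose values are taken on Day 1 of each period

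*SAP*

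**What the plan says.** SAP 7.2.3 sets one rule: "Screening visit will be used as a baseline for all post baseline variables". The protocol has the same rule for vital signs in 8.4.5.2: "Vital signs (systolic and diastolic BP and HR) at each visit and change from baseline (screening value) in each vital sign" is to be summarised descriptively. For the laboratory, SAP 8.5.2 reads: "Laboratory values and changes from baseline (screening value) in laboratory values will be summarised using descriptive statistics". Protocol 8.4.5.3 and SAP 8.5.3 agree with these. The SAP's list of safety tables adds "Shift tables for haematology variables", with counterparts for chemistry and urinalysis. None of them names another baseline, so the general rule applies.

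The schedule provides a later pre-dose value. Protocol 6.1.2, on the treatment periods, has for Day 1: "BP and HR will be recorded in the supine position after at least 5 min rest 0-2 h before the first morning dose". Protocol 6.4.5 has for the laboratory: "The following selected laboratory tests will be performed on days 1 and 7 in each treatment period, before the first dose". Urinalysis is part of that Day 1 and Day 7 set. Neither document says why these values are not used as a baseline.

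On timing, Protocol 3.2 says: "All groups will have a crossover design with 4 treatment periods, each lasting for 8 days". Protocol 6.1.1 says: "The screening visit will take place within 21 days before the first study treatment administration". Protocol 1.2.1 sets a wash-out of at least 4 days and justifies it by elimination of the three drugs, without reference to recovery of blood pressure, heart rate or laboratory values.

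**The concern.** In a crossover, a by-treatment change table is meant to show what happened under that treatment. If every change starts from one visit before period 1, the entry for a treatment given in period 3 or 4 also contains what happened in between: the passage of time, earlier blood sampling (32 PK samples per period, Protocol 6.2.1), regression from a screening visit at which heart rate and blood pressure had to lie within limits (Protocol 4.3), and any effect of the preceding treatment that has not recovered.

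The last item matters most. Protocol 1.3 names increased liver tests as an important potential risk of ODM-104. The Day 7 laboratory sample is taken before that day's doses, so the next scheduled one is on Day 1 of the following period or at the end-of-study visit. A rise that began under ODM-104 and persisted would enter the change and shift tables of the next treatment, which may not contain ODM-104.

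**Working it through.** The plan gives no figure on this point, so there is none to reproduce.

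**Inputs.** Screening 0-21 days before first dose (Protocol 6.1.1). Four periods with dosing on Days 1-7 (3.2, 5.3). Wash-out of at least 4 days (1.2.1). Total duration 10-15 weeks (3.2). End-of-study visit 4-21 days after the last dose (6.1.3). Group 1 example sequences BCAD, ABDC, DACB, CDBA (5.4, Table 2), where C and D contain ODM-104. 14 subjects per group (4.1).

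**1. Gap from baseline to Day 7.** At the minimum wash-out, Day 1 to the next Day 1 is 6 + 4 = 10 days. The gap in period p is (0 to 21) + 10(p - 1) + 6 days:

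- Period 1: 6-27
- Period 2: 16-37
- Period 3: 26-47
- Period 4: 36-57

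Longer wash-outs lengthen the gaps in periods 2-4. If the 10-15 weeks run from screening to the end-of-study visit, screening to last dose is 70 - 21 = 49 to 105 - 4 = 101 days. With a same-period Day 1 baseline the gap is 6 days in every period.

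**2. Common drift.** Suppose a drift of 1 unit per period, counted from screening. With equally filled sequences each treatment stands once in each position, so each gets (1 + 2 + 3 + 4)/4 = 2.5 units. Fourteen subjects cannot fill four sequences equally. With 3, 4, 4 and 3 subjects in the order listed, A gets (3×3 + 4×1 + 4×2 + 3×4)/14 = 33/14 = 2.36 and C gets (3×2 + 4×4 + 4×3 + 3×1)/14 = 37/14 = 2.64. Over all 4/4/3/3 splits the range is 2.36-2.64. The absolute change is shifted by about 2.5 units and contrasts by at most 0.28 units.

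**3. Carry-over.** Let an ODM-104 treatment leave a residual c at the next Day 1 that persists in full to Day 7. The immediate predecessors, in sequence order, are:

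- A: C, none, D, B, so 2 of 4 contain ODM-104
- B: none, A, C, D, so 2 of 4
- C: B, D, A, none, so 1 of 4
- D: A, B, none, C, so 1 of 4

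With equal filling, the screening baseline adds 0.50c to A and B but 0.25c to C and D. The contrast of ODM-104 against no ODM-104 narrows by 0.50c - 0.25c = 0.25c. A Day 1 baseline removes this residual.

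If only a fraction p of c remains on Day 7, a period that follows ODM-104 is charged +pc with a screening baseline and -(1 - p)c with a Day 1 baseline. The two are equal in size at p = 0.5. Below that, the Day 1 baseline has the larger bias, and it looks like an improvement.

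**4. Precision.** In units of the between-subject SD, a change has SD √(2(1 - r)). Assuming r = 0.6 with screening and 0.8 with same-period Day 1 gives 0.89 and 0.63, a 29% reduction for the change within one treatment. In a contrast the screening value S cancels: (A - S) - (D - S) = A - D, with variance 2(1 - 0.6) = 0.8 if the between-period correlation is also 0.6. With period baselines and equal between-period correlations the variance is 2 × 2(1 - 0.8) = 0.8, so nothing is gained. At a between-period correlation of 0.7 the screening contrast has variance 0.6 and the period-baseline contrast is the noisier one.

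**The case against.** The strongest reply is that little of this reaches a treatment comparison. One screening value per subject cancels within subject. Drift nearly balances across the Williams sequences. Regression from screening is the same quantity in all four periods, and the screening limits are two-sided. Carry-over needs an effect that outlasts at least 4 days; Protocol 1.3 mentions only isolated, mild transaminase increases, and no recovery time is given. Several outputs do not use a baseline at all: actual values, out-of-range counts by visit, and individual listings. The analyses are descriptive, and protocol and SAP agree with each other. All of this stands.

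It also stands that Day 1 as the only baseline would do harm in periods 2-4. A persisting elevation would become the new baseline and read as high-to-high in a shift table, and a partial recovery would read as improvement.

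What the reply does not answer is that the planned tables report within-treatment changes and shifts, where drift does not cancel, and that unrecovered carry-over does not cancel between treatments either. The haematology template splits by treatment and period, but with one row per period it does not separate Day 1 from Day 7.

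Two stronger readings are tempting. One is that a Day 1 baseline would sharpen treatment comparisons; step 4 shows that this does not follow. The other is to turn the PK sampling into a haemoglobin fall. The documents provided give no sample volume (Protocol 6.2.1 places the maximum in the subject information), so any figure would be a ceiling built on assumed volumes and no replacement, not an estimate.

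**Conclusion.** The point holds for the descriptive tables. Screening is the only baseline for vital-sign and laboratory changes and laboratory shifts in all four periods, and at the minimum wash-out it lies 36-57 days before Day 7 of period 4. In periods 2-4 the changes include drift, and an unrecovered effect of the previous treatment is attributed to the next one.

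Drift and regression from screening mainly distort absolute changes. Only carry-over biases contrasts, by 0.25c under equal filling of the example sequences and full persistence to Day 7. The size of c is unknown.

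A reader might infer that a liver signal of ODM-104 would be missed, or that the study's conclusions are at risk. The documents do not support that: there is no evidence of an effect lasting beyond the wash-out, outputs that need no baseline are planned, and no PK conclusion depends on these tables. The ECG baseline is a separate question and is not part of this point.

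**What to change.** In SAP 7.2.3, 8.5.2 and 8.5.3, and in Protocol 8.4.5.2 and 8.4.5.3:

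- Use the Day 1 pre-dose value of the same period as baseline for in-period changes in vital signs and the selected laboratory tests, and for in-period shifts in the selected tests and urinalysis.
- Show Day 1 and Day 7 as separate rows in the laboratory tables.
- Keep the screening-based change and shift tables as supplementary, so that cumulative or persisting elevations stay visible.
- Keep screening as baseline for the end-of-study visit and for analytes without a Day 1 value (serum glucose and calcium; albumin and thyroid stimulating hormone are scheduled only at screening).

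No new data are needed. The cost is programming, the text changes and an extra set of tables. The Day 1 tables should not be read alone, because they can mask a persisting elevation or show recovery as improvement; the supplementary tables guard against this.

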1.2.1 Rationale of the study design

A crossover design was chosen for this study in order to reduce the impact of inter-individual variability on levodopa PK parameters. This design has been previously used successfully in similar PK studies. Open-label study drug administration is regarded appropriate, because the primary study variables are PK parameters derived from drug concentrations in plasma. Administration of carbidopa and COMT inhibitor for 6 days before levodopa administration will ensure clinically adequate AADC and COMT inhibition when assessing levodopa PK on day 7. There will be a wash-out period of at least 4 days between the study treatment administrations. The length of the wash-out period is considered sufficient for the elimination of levodopa, carbidopa and ODM-104.

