6. STUDY PROCEDURES AND ASSESSMENTS

6.1 Study procedures

Table 3 lists all study procedures and indicates with an 'x' during which visit a particular procedure is performed.

Table 3. Schedule of study events

Protocol activities	Screening	Treatment period						End-of-study
	≤21 days before first dose	Day -1	Day 1	Days 2-5	Day 6	Day 7	Day 8	4-21 days from last dose
IC ¹								
Physical examination	X							X
Demography and substance use	X							
Use of nicotine	X	X						
Weight and BMI	X							X
Height	X							
Vital signs: BP and HR	X	X	X ²		X ³	X ⁴		X
12-lead ECG	X	X	X ^{2,5}		X ⁶	X ⁷		X
Laboratory assessments								
• Haematology and clinical chemistry	X		X ^{2,8}			X ⁸		X ⁹
• Urinalysis	X		X ²			X		X
• Serology	X							
Alcohol breath test	X	X						
Urine drug abuse test	X	X						
C-SSRS	X					X		
Decision of entry	X							
Study treatments, 4 times a day								
Carbidopa					X			
ODM-104					X ¹⁰			
Levodopa						X		
Blood samples for PK						X	X	
Blood sample for PG								X ¹¹
Medical history and current medical conditions								Continuously
AEs								Continuously
Concomitant treatments								Continuously

¹ IC for the main study before any screening activities; for the optional PG IC, see footnote 11

² On day 1: 0-2 h before the first dose

Vital signs in supine position after 5 min rest:

³ On day 6: 1-2 h after the 7 h dose

⁴ On day 7: 0-2 h before the first dose and at 1-2 h after the 7 h dose

12-lead ECG in supine position after 5 min rest

⁵ On day 1: 0-2 h before the first dose - 3 recordings within 5 min, 1-2 min interval between the measurements

⁶ On day 6: 1-2 h after the 7 h dose

⁷ On day 7: 0-2 h before the first dose and 1-2 h after the 7 h dose

⁸ Selected laboratory tests before the first dose of the day

⁹ The same laboratory tests as at the screening visit except thyroid stimulating hormone and albumin

¹⁰ Only in treatment periods including ODM-104

¹¹ PG (optional): The sample is taken once from subjects who have signed the PG IC

C-SSRS = Columbia-Suicide Severity Rating Scale; PG = pharmacogenomics

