6.4.4 Clinical safety assessments

HR, PB and 12-lead ECG will be recorded in the supine position after at least 5 min rest. The time points at which HR, BP and 12-lead ECG are recorded ECG are presented in [Table 3](#).

12-lead ECG will be recorded 3 times within 5 min (1-2 min interval between the measurements) on day 1 pre-dose. The mean of 3 separate 12-lead ECG recordings will be considered as a baseline.

All 12-lead ECG data collected will be stored. Decision on whether or not to analyse all data will be made during or after the study. If additional ECG analysis will be performed, the results may be reported in a separate report.

A physical examination will be performed by the investigator at screening and end-of-study.

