|           | Period 1 DAY 7: 0-2 H BEFORE FIRST DOSE | X | X.XX   | XX.XX | -X.X    | X.XX   | XX.X    |
|           | Period 1 DAY 7: 1-2 H AFTER 7 H DOSE    | X | X.XX   | X.XX  | -X.X    | -X.XX  | XX.X    |
|           | Period 2 DAY -1                         | X | X.XX   | X.XX  | -X.X    | X.XX   | X.X     |
|           | Period 2 DAY 1: 0-2 H BEFORE FIRST DOSE | X | .      | .     | .       | .      | .       |
|           | Period 2 DAY 6: 1-2 H AFTER 7 H DOSE    | X | -X.XX  | XX.XX | -XX.X   | -X.XX  | XX.X    |
|           | Period 2 DAY 7: 0-2 H BEFORE FIRST DOSE | X | X.XX   | X.XX  | -X.X    | X.XX   | XX.X    |
|           | Period 2 DAY 7: 1-2 H AFTER 7 H DOSE    | X | X.XX   | X.XX  | -X.X    | X.XX   | XX.X    |
|           | Period 3 DAY -1                         | X | -XX.XX | XX.XX | -XX.X   | -XX.XX | -X.X    |
|           | Period 3 DAY 1: 0-2 H BEFORE FIRST DOSE | X | .      | .     | .       | .      | .       |
|           | Period 3 DAY 6: 1-2 H AFTER 7 H DOSE    | X | -X.XX  | X.XX  | -XX.X   | -X.XX  | X.X     |
|           | Period 3 DAY 7: 0-2 H BEFORE FIRST DOSE | X | -X.XX  | X.XX  | -XX.X   | X.XX   | X.X     |
|           | Period 3 DAY 7: 1-2 H AFTER 7 H DOSE    | X | -X.XX  | XX.XX | -XX.X   | -X.XX  | X.X     |
|           | Period 4 DAY -1                         | X | X.XX   | XX.XX | -X.X    | -X.XX  | XX.X    |
|           | Period 4 DAY 1: 0-2 H BEFORE FIRST DOSE | X | .      | .     | .       | .      | .       |
|           | Period 4 DAY 6: 1-2 H AFTER 7 H DOSE    | X | X.XX   | XX.XX | -XX.X   | -X.XX  | XX.X    |
|           | Period 4 DAY 7: 0-2 H BEFORE FIRST DOSE | X | -X.XX  | X.XX  | -XX.X   | X.XX   | X.X     |
|           | Period 4 DAY 7: 1-2 H AFTER 7 H DOSE    | X | -X.XX  | X.XX  | -XX.X   | X.XX   | X.X     |

Screening value is considered as baseline

Program: T\_14\_3\_7\_2\_2\_Change from bl in PR interval.sas

Date: 23MAY17:09:10

STUDY 3112005

DRAFT

Page: 1 (4)

Table 14.3.1.9 Suicidality assessment by C-SSRS during treatment  
Safety population

|   |    | A1
(N=13) |        | B1
(N=14) |        | C1
(N=14) |        | D1
(N=13) |        |
|---|----|--------------|--------|--------------|--------|--------------|--------|--------------|--------|
|   |    | n            | (%)    | n            | (%)    | n            | (%)    | n            | (%)    |

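### The protocol gives two ECG baselines and the SAP adopts screening, so the day 1 pre-dose triplicate is not the reference for any planned ECG change output

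*SAP*

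**What the plan says.** Two current sections of the protocol define the ECG baseline differently.

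- **Protocol 6.4.4** places three recordings before dosing on day 1 and continues: "The mean of 3 separate 12-lead ECG recordings will be considered as a baseline". The schedule of events (Protocol 6.1, Table 3, footnote 5) puts them in the treatment-period column: "On day 1: 0-2 h before the first dose - 3 recordings within 5 min, 1-2 min interval between the measurements". Section 6.1.2.1 repeats this among the treatment-period procedures.
- **Protocol 8.4.5.2**, the analysis section, says: "12-lead ECG parameters at each time point and change from baseline (screening value) will be summarised using descriptive statistics".

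The SAP follows the second definition throughout. Section 7.2.3 sets the general rule, "Screening visit will be used as a baseline for all post baseline variables", and section 8.5.3 repeats screening for ECG. The footnote to the one ECG change template shown (Table 14.3.7.2.2, PR interval) reads: "Screening value is considered as baseline". SAP 7.2.3 does average repeated ECGs, but only those recorded at screening, and Protocol 6.1.1 schedules no replicates at that visit.

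SAP 8.7, the place for departures from the protocol, is a heading without text. Protocol 4.5 stops treatment for a QTc rise above 60 ms or a QRS rise above 25% from baseline, without saying which baseline.

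**The concern.** A scheduled pre-dose triplicate normally serves to give a stable reference close to dosing, and Protocol 6.4.4 assigns it that purpose. Under the SAP it is summarised at most as one more time point. Each ECG change, and each QTcF change-category count in Table 14.3.7.10.2, is then taken from an older reading that is normally single.

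This matters more for ECG than for most safety variables here. Protocol 1.3 names cardiac arrhythmias as an important potential risk of ODM-104 and mentions isolated conduction abnormalities in earlier studies. The PR, QRS and QTcF changes are the outputs that address this. In addition, an investigator applying Protocol 4.5 could use the triplicate while the report uses screening, so the change that stopped a subject might not match the change tabulated for him.

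**Working it through.** The documents state no figure to reproduce. The check covers which outputs are affected, how far apart in time the two references are, and how the two definitions differ.

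**1. Outputs affected (SAP 10.1).**
- Change tables: PR (14.3.7.2.2), QRS (14.3.7.3.2), RR (14.3.7.4.2), QT (14.3.7.5.2), QTcF (14.3.7.7.2), QT categories (14.3.7.8.2) and QTcF categories (14.3.7.10.2), 7 in all.
- Change figures: PR, QRS, RR, QT, QTcB and QTcF (14.4.8.2 to 14.4.13.2), 6 in all.
- The ECG shift table (14.3.7.1.2) also needs a baseline and is not in this count.

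**2. Age of each reference at the day 7 ECG.** Inputs:
- Protocol 6.1.1: "The screening visit will take place within 21 days before the first study treatment administration"
- Protocol 1.2.1: "There will be a wash-out period of at least 4 days between the study treatment administrations"
- Protocol 5.3: doses at 08:00, 11:30, 15:00 and 18:30.

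The last dose of a period is at 18:30 on day 7. Four full days later is 18:30 on day 11, so the earliest next 08:00 first dose is on day 12. The shortest cycle is therefore 11 days. If screening is *s* days before first dose, the gap from screening to day 7 of period *k* is *s* + 6 + 11(*k* − 1).

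| Period | Screening, *s* = 21 | Screening, *s* = 1 | Same-period triplicate |
|---|---|---|---|
| 1 | 21 + 6 + 0 = 27 days | 1 + 6 + 0 = 7 days | 7 − 1 = 6 days |
| 2 | 21 + 6 + 11 = 38 days | 18 days | 6 days |
| 3 | 21 + 6 + 22 = 49 days | 29 days | 6 days |
| 4 | 21 + 6 + 33 = 60 days | 40 days | 6 days |

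A longer wash-out widens the screening gaps from period 2 onwards and leaves the triplicate gap unchanged.

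**3. Difference between the definitions.** For one man in one period:

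(on-treatment − screening) − (on-treatment − day 1 mean) = day 1 mean − screening.

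This offset applies equally to every on-treatment ECG of that period: one on day 6 and two on day 7, so 3 per period and 3 × 4 = 12 per man.

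**4. Possible size.** The documents give neither the offset nor any ECG variance. If the offset were 5 to 15 ms for QTcF (assumption), the reported change would move by that amount: 5/60 = 8.3% to 15/60 = 25% of the 60 ms limit in Protocol 4.5. The SAP does not state the cut-offs for Table 14.3.7.10.2, so the stopping limit is only a yardstick.

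**5. Precision (illustration only).** Assume equal variance for every single ECG and independence between occasions. Let *f* be the share of single-ECG variance that replicate averaging can reduce. The SD of change from a triplicate mean, relative to change from a single ECG, is √((2 − 2*f*/3)/2). This gives 1.00 at *f* = 0, √(1.667/2) = 0.91 at *f* = 0.5 and √(1.333/2) = 0.82 at *f* = 1.

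**The case against.** The strongest reply is that the two protocol sentences can coexist. Section 6.4.4 describes assessments and calls the triplicate mean one baseline among possible others. It then allows further ECG analysis to be decided later and reported separately. Section 8.4.5.2 governs the tables, and the SAP follows it almost word for word. On that view the drafters had nothing to record in SAP 8.7, and the triplicate might serve the stopping limits. This reading is possible, but no sentence states it. The deferral in 6.4.4 concerns whether to analyse all stored ECG data, not which baseline the planned tables use.

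The template is also less clear than its footnote. In Table 14.3.7.2.2 the day 1 pre-dose rows show only dots in all four periods, while the day −1, day 6 and day 7 rows have placeholders for values. A change from screening could be computed on day 1, so the programming may have treated day 1 as a reference or may have left the triplicate unprocessed. That makes the actual programming less certain, but the footnote and both SAP sections still say screening.

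Several mitigating points stand:
- Values are summarised at each time point, so with complete data a mean change from day 1 can be found by subtracting table means. Its spread and category counts cannot.
- Individual ECGs are listed (16.2.9.3), stopped cases are captured as adverse events, and the synopsis plans to evaluate within-subject differences between visits for ECG abnormalities.
- Screening is drug-free and is also the baseline for vital signs and laboratory values.
- A man's screening value is common to his four periods, so mean differences between treatments change little.

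**Conclusion.** The concern holds. The protocol contradicts itself on the ECG baseline, and the SAP resolves this without comment in favour of screening. As written, none of the 7 change tables or 6 change figures uses the triplicate as its reference.

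The time gaps (27 to 60 days with the earliest screening, 7 to 40 with screening one day before, against 6 days) rest on a minimum wash-out of four full days. They show how remote the reference is and do not by themselves demonstrate bias. The per-man shift is exact in form but unknown in size; 5 to 15 ms is an assumption.

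The effect falls on individual changes and change-category counts, where the offset does not cancel, and on whether reported changes match those used for stopping. It is limited to descriptive safety reporting and leaves the pharmacokinetic analyses untouched. It should be corrected because the better baseline is scheduled and the protocol itself already calls it the baseline.

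**What to change.** **SAP.** In 7.2.3 and 8.5.3 and the ECG change-table footnote, define the ECG baseline as the mean of the three day 1 pre-dose recordings of the same period. Protocol 6.4.4 does not specify per period; that choice follows from Table 3 and 6.1.2.1, which place the triplicate among the treatment-period procedures. Apply the same rule to shift table 14.3.7.1.2. Keep change from screening as a supportive output, so that a shift persisting across periods stays visible and the day −1 and end-of-study rows have a reference. Record the decision in SAP 8.7.

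**Protocol.** Bring 8.4.5.2 into line with 6.4.4. Separately, state at the next amendment which baseline the Protocol 4.5 limits use. That decision need not match the tables, because a per-period baseline would reset the limit in every period. The SAP templates carry a program date of May 2017 and the protocol planned a start in February 2017. If dosing is already complete, the 4.5 change no longer matters, but the SAP correction still does.

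**Cost.** A few sentences in the SAP and reprogramming of 7 tables, 6 figures and the shift table. The protocol wording needs an amendment, with ethics committee and competent authority approval if it is substantial. No new data are required.
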